1.3.3 Thalidomide - Toxicity

Available data from three clinical pharmacology studies sponsored by Celgene Corporation showed that 38 subjects have been exposed to single doses of thalidomide given either on one occasion or three occasions with one to two week washouts between doses. Two studies were conducted in healthy volunteers and the third study was conducted in patients with Hansen's disease. Thalidomide was administered in a 50 to 400 mg single dose range.

Based on the results of the studies, the most frequently reported adverse experiences were dizziness (31 subjects or 82 %), somnolence (29 subjects or 76%), headache (15 subjects or 39%), and asthenia (12 subjects or 32%). Somnolence and dizziness were reported to occur more frequently at doses of 200 mg and 400 mg than they did at a dose of 50 mg. There was no dose relationship evident for the remaining adverse experiences.

There was no reported severity in intensity of all adverse experiences. All events were mild with the exception of moderate somnolence in 13 subjects, moderate dizziness in 6 subjects, moderate headache in 4 subjects, moderate hypotension in 2 subjects and moderate constipation and moderate pallor in 2 subjects, and a single report of moderate asthenia, diarrhea, leg cramps, nausea and rhinitis. There have been reports of a slowing of the heart rate.

Thalidomide is known to cause nerve damage that may be permanent. Peripheral neuropathy is a common, potentially severe, side effect of treatment with thalidomide that may be irreversible. Peripheral neuropathy generally occurs following chronic use over a period of months, however, reports following short-term use also exist. The correlation with cumulative dose is unclear. Patients should be examined at monthly intervals for the first three months of thalidomide therapy to enable the clinician to detect early signs of neuropathy, which include numbness, tingling or pain in the hands and feet. Patients should be evaluated periodically thereafter during treatment. If symptoms of drug-induced neuropathy develop, thalidomide should be discontinued immediately to limit further damage, if clinically appropriate. Usually treatment with thalidomide should only be reinitiated if the neuropathy returns to baseline status.

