Serious dermatologic reactions including toxic epidermal necrolysis and Stevens-Johnson syndrome, which may be fatal, have been reported in association with thalidomide therapy. THALOMID® should be discontinued, if a skin rash occurs and only resumed following appropriate clinical evaluation. If the rash is purpuric, vasculitic, exfoliative, or bullous or if Stevens-Johnson syndrome or toxic epidermal necrolysis is suspected, use of THALOMID® should not be resumed.

The use in Thalidomide in Multiple Myeloma results in an increased risk of venous thromboembolytic events, such as deep vein thrombosis and pulmonary embolus. The risk increases significantly when thalidomide is used in combination with standard chemotherapeutic agents including dexamethasone. In one controlled trial the rate of venous thromboembolic events was 22.5% in patients receiving thalidomide in combination with dexamethasone compared to 4.9% receiving dexamethasone alone. Patients and physicians are advised to be observant for signs of thromboembolism. Patients should seek medical attention should they develop symptoms such as shortness of breath, chest pain or leg or arm swelling. Preliminary reports suggest that patients who are appropriate candidates may benefit from concurrent prophylactic anticoagulation or aspirin treatment.

Although not reported from pre-marketing controlled clinical trials, seizures, including grand mal convulsions, have been reported during post-approval use of THALOMID® (thalidomide) in clinical practice. Because these events are reported voluntarily from a population of unknown size, estimates of frequency cannot be made. Most patients had disorders that may have predisposed them to seizure activity, and it is not currently known whether thalidomide has any epileptogenic influence. During therapy with thalidomide, patients with a history of seizures or with other risk factors for the development of seizures should be monitored closely for clinical changes that could precipitate acute seizure activity.

THALOMID®(thalidomide) can cause severe birth defects in humans. Women and men taking thalidomide must take special precautions and be willing and able to comply with all aspects of the FDA-mandated S.T.E.P.S.® program. (see Appendix A: Risks of Fetal Exposure, Pregnancy Testing Guidelines and Acceptable Birth Control Methods)

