\geq Grade 2	Muscle weakness	
 ▪ Decrease dose by 1 dose level ▪ If symptoms persist then decrease by dosing by 1 dose level as needed
\geq Grade 3	Hyperglycemia	
 ▪ Decrease dose by 1 dose level ▪ Treat with insulin or oral hypoglycemics as needed
\geq Grade 3	Acute pancreatitis	
 ▪ Discontinue subject from dexamethasone

Side effects associated with high-dose dexamethasone therapy include the following:

- Gastrointestinal: nausea, vomiting, anorexia, increased appetite, weight gain, aggravation of peptic ulcers
- Dermatologic: rash, skin atrophy, facial hair growth, acne, facial erythema, ecchymoses
- Genitourinary: menstrual irregularities, amenorrhea
- Neurologic: insomnia, euphoria, psychosis, headache, vertigo, depression, seizures, muscle weakness
- Cardiovascular: fluid retention, edema, hypertension, thrombophlebitis
- Ocular: cataracts, increased intraocular pressure, exophthalmos
- Metabolic: hyperglycemia, aggravation or precipitation of diabetes mellitus, adrenal suppression (with Cushingoid features), hypokalemia
- Hematologic: leukocytosis
- Other: osteoporosis, infection (including herpes zoster, varicella zoster, fungal infections, pneumocystis carinii, tuberculosis), muscle wasting, delayed wound healing, and suppression of reactions to skin tests.

Dexamethasone may be dose modified due to toxicity at the discretion of the treating physician as follows:

- Starting dose: dexamethasone 40 mg by mouth on days 1-4, 9-12 and 17-20 of each 28 day treatment cycle for cycle 1.

- During Cycle 2, 20 mg by mouth on days 1-4, 9-12, and 17-20.
For all cycles beyond 2:
- Dose level -1: dexamethasone 20 mg/m² po on Days 1, 8, 15 and 22.
- Dose level -2: dexamethasone 20 mg po on Days 1, 8, 15, and 22.
- Dose level -3: dexamethasone 20 mg po on Days 1 and 15.

Dose Modification Guidelines for Thalidomide:

1. Grade 1-2 AE the dose will be continued at the investigators discretion.
2. Grade 3 or higher AEs related to study drug, dose will be held until AE returns to grade 2 or less. If grade 3 AE occurs a second time the dose will be held until the AE decreases to grade 2 or less. Thalidomide will be restarted at 50% of previous dose. If grade 3 AE occurs a third time drug will be discontinued and the pt followed until the AE resolves or stabilizes.

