3. For neurotoxicity for grade 2 toxicity or higher, hold drug until symptoms subside to baseline, grade 1 or less and then Thal may be restarted at 50% of previous dose. If neuropathy develops again with either Thal another 50% reduction can occur after symptoms resolve to 50 mg every day or every other day.
4. For grade 2 constipation Senna will be added to sodium docusate.
5. For somnolence the dose of Thalidomide should be held until symptoms resolve and then will be reduced 50%.

International Myeloma Working Group uniform response criteria:

Response Subcategory	Response criteria
sCR	CR as defined below plus Normal FLC ratio and Absence of clonal cells in bone marrow ^b by immunohistochemistry or immunofluorescence ^c
CR	Negative immunofixation on the serum and urine and Disappearance of any soft tissue plasmacytomas and \leq 5% plasma cells in bone marrow ^b
VGPR	Serum and urine M-protein detectable by immunofixation but not on electrophoresis of 90% or greater reduction in serum M-protein plus urine M-protein level < 100 mg per 24 h
PR	\geq 50% reduction of serum M-protein and reduction in 24-h urinary M-protein by \geq 90% or to < 200 mg per 24h If the serum and urine M-protein are unmeasurable, ^d a \geq 50% decrease in the difference between involved and uninvolved FLC levels is required in place of the M-protein criteria. If serum and urine M-protein are unmeasurable, and serum free light assay is also unmeasurable, \geq 50% reduction in plasma cells is required in place of M-protein, provided baseline bone marrow plasma cell percentage was \geq 30% In addition to the above listed criteria, if present at baseline, a \geq 50% reduction in the size of soft tissue plasmacytomas is also required
SD (not recommended for use as an indicator of response; stability of disease is best described by providing the time to progression estimates)	Not meeting criteria for CR, VGPR, PR or progressive disease

Abbreviations: CR, complete response; FLC, free light chain; PR, partial response; SD, stable disease; sCR, stringent complete response; VGPR, very good partial response.

^a All response categories require two consecutive assessments made at anytime before the institution of any new therapy; all categories also require no known evidence of progressive or new bone lesions if radiographic studies were performed. Radiographic studies are not required to satisfy these response requirements.

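### Thalidomide rule 2 in Appendix B has no rash exception and so permits a restart after severe rash types for which section 1.3.3 says the drug should not be resumed

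*Combined protocol and SAP*

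**What the plan says.** Section 1.3.3 (Thalidomide - Toxicity) gives the reason for concern: "Serious dermatologic reactions including toxic epidermal necrolysis and Stevens-Johnson syndrome, which may be fatal, have been reported in association with thalidomide therapy". It then gives two instructions. For any rash: "THALOMID® should be discontinued, if a skin rash occurs and only resumed following appropriate clinical evaluation". For severe forms, it sets this condition and action: "rash is purpuric, vasculitic, exfoliative, or bullous or if Stevens-Johnson syndrome or toxic epidermal necrolysis is suspected, use of THALOMID® should not be resumed".

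Appendix B has five numbered rules for thalidomide. Rule 1 is generic: "Grade 1-2 AE the dose will be continued at the investigators discretion". Rule 2 is also generic: "Grade 3 or higher AEs related to study drug, dose will be held until AE returns to grade 2 or less". On a second Grade 3 event it holds the drug again and restarts it at half the previous dose. Its last step is "If grade 3 AE occurs a third time drug will be discontinued and the pt followed until the AE resolves or stabilizes". Rules 3, 4 and 5 cover neurotoxicity, constipation and somnolence.

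The main table of Appendix B has three skin rows: non-blistering rash, desquamating rash and erythema multiforme. Every action in them that names a drug names lenalidomide.

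**The concern.** A site dealing with a skin reaction is likely to turn to the dose-modification appendix. For thalidomide it finds no rash rule there and falls back on the generic ones. For the severe rash types, those rules describe a hold-and-restart path where the protocol's own toxicity section says the drug should stay off. Sections 6.8.3, 6.11 and 6.12 do not point back to section 1.3.3. At stake is rechallenge with thalidomide after a reaction that the protocol describes as possibly fatal.

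It looks like an omission, since no reason is given for treating the two drugs differently. Read literally, a Grade 2 blistering rash stops lenalidomide permanently while rule 1 lets thalidomide continue at discretion.

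**Working it through.** No formula applies; the check sets the texts side by side. In what follows, the listed reactions are the four severe rash types in section 1.3.3 plus suspected Stevens-Johnson syndrome or toxic epidermal necrolysis.

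1. **Does any thalidomide rule name rash?** Rules 1 and 2 are generic, and rules 3 to 5 each name another toxicity. Count: 0 of 5.

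2. **Listed reaction, Grade 3 or higher, related.** Section 1.3.3: do not resume, whatever the recovery. Rule 2, step by step for Grade 3 events:
   - First event: hold until Grade 2 or less. A restart is not stated, but holding until a threshold, and then providing for a second event, implies one.
   - Second event: hold, then restart at 50%. This restart is explicit.
   - Third event: discontinue.

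   Restarts permitted: 1 implied + 1 explicit = 2 under rule 2, against 0 under section 1.3.3.

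3. **Listed reaction, Grade 1-2.** Section 1.3.3 still says not to resume, since it goes by type of rash and not by grade. Rule 1 leaves continuation to discretion.

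4. **Ordinary mild rash.** Section 1.3.3 stops the drug but allows it back after evaluation; rule 1 leaves continuation to discretion. The gap is only whether the drug is held while the rash is assessed.

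5. **Does another section close the gap?**
   - Section 6.3.2 lets therapy be held and continued on recovery.
   - Section 6.3.3 requires recovery to Grade 1 or baseline before a new cycle. That is stricter than rule 2, but it governs cycle starts. Thalidomide is taken daily (section 6.8.3), so a restart can arise within a cycle, and a bullous rash that has cleared meets the criterion.
   - Section 6.12 permits a stop on investigator judgment; it does not name rash or bar rechallenge.
   - Exclusion criterion 5 concerns a past desquamating reaction at entry, not a rash on study.

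   None bars resumption after a listed reaction.

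6. **Comparison with neuropathy.** Section 1.3.3 has one other toxicity stop: "If symptoms of drug-induced neuropathy develop, thalidomide should be discontinued immediately to limit further damage, if clinically appropriate". Appendix B gives it a rule of its own: "For neurotoxicity for grade 2 toxicity or higher, hold drug until symptoms subside to baseline, grade 1 or less". So one of the two stop instructions has a specific thalidomide rule and rash does not. The comparison shows only that: rule 3 starts at Grade 2, so it does not fully match section 1.3.3 either.

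**The case against.** The strongest reply is that the safeguard is already in the protocol. Section 1.3.3 names the drug and gives direction, and nothing in rules 1 and 2 claims to override it. Reading the specific text over the generic resolves the conflict and leaves only a missing cross-reference. Discretion adds further protection. Appendix B is headed as suggested guidance. Section 6.11 says the same, although it cites Appendix C. Section 6.12 ends treatment for events that the investigator judges could do severe or lasting harm, which suspected Stevens-Johnson syndrome or toxic epidermal necrolysis would readily meet.

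Much of this stands, and it keeps the point minor. A reader might infer that the protocol has no thalidomide stop for rash, or that it obliges sites to rechallenge; the documents support neither. A reader might also take rule 1 to contradict section 1.3.3 for every rash. For ordinary mild rash it does not go that far: stopping complies with rule 1, and section 1.3.3 itself allows resumption after evaluation.

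What the reply does not remove is that rule 2, followed as written, gives a less safe action than section 1.3.3 for the listed reactions, and no operational section says which text governs.

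**Conclusion.** The inconsistency is real for the listed reactions and is a minor patient-safety drafting point. Rule 2 permits thalidomide to be restarted where section 1.3.3 says it should not be, and rule 1 leaves continuation at Grade 1-2 to discretion. The conclusion assumes that a reaction not named in the thalidomide list falls under the generic rules and, for rule 2, that the reaction is judged related to study drug.

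The count of two restarts against none should not be read as two stated restarts: only the one at half dose is written out. Nor does it predict what investigators would do. The documents give no rate of bullous or exfoliative rash, Stevens-Johnson syndrome or toxic epidermal necrolysis on this combination, so expected cases cannot be estimated. A reader might suspect a knock-on effect on the maximum tolerated dose, the sample size or the stopping boundaries; nothing in the documents shows one.

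**What to change.** Add one rule to the thalidomide list in Appendix B, stated to take precedence over rules 1 and 2: *For skin rash, hold thalidomide and restart only once the rash has been clinically evaluated. For purpuric, vasculitic, exfoliative or bullous rash, or suspected Stevens-Johnson syndrome or toxic epidermal necrolysis, discontinue thalidomide and do not restart it.* This moves the protocol's own instruction to the place where dosing decisions are made. Making it mandatory, outside the discretion in section 6.11, would go further than section 1.3.3, which is itself worded as a recommendation; alignment does not need it.

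The cost is one line in an amendment, slightly less dosing discretion, and a few missed thalidomide doses while a mild rash is evaluated. No new data are needed.

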6.2 Phase I Portion

To determine the MTD of the combination of thalidomide, lenalidomide and dexamethasone (LTD), with 4 dose levels planned. Dosing will start at doses of LTD that are intermediate intensity because of overlapping side effect profile of lenalidomide and thalidomide to determine the MTD and maximize the overall response rate of the regimen.

Table 6-1 Dose Levels to be studied

Dose Level	Assigned Therapy
Level -1	15 mg Lenalidomide daily on days 1-21 followed by 7-day rest every 28 days 50 mg Thalidomide daily 40 mg dexamethasone *
Level 1	15 mg Lenalidomide daily on days 1-21 followed by 7-day rest every 28 days 100 mg Thalidomide daily 40 mg dexamethasone *
Level 2	25 mg Lenalidomide daily on days 1-21 followed by 7-day rest every 28 days 100 mg Thalidomide daily 40 mg dexamethasone *
Level 3	25 mg Lenalidomide daily on days 1-21 followed by 7-day rest every 28 days 200 mg Thalidomide daily 40 mg dexamethasone

* Dexamethasone dosing for cycle 1-2: 40 mg days 1-4, 9-12, and 17-20; all subsequent cycles: 40 mg days 1,8, 15, 21

Dose Escalation

The first cohort of three patients enrolled into the study will receive dose level 1. A full safety evaluation will be conducted when these subjects have completed one cycle (28 days) of combination therapy.

Definition of DLT

A DLT will be defined as follows:

- Hematologic dose-limiting toxicity will be defined as either Grade 4 neutropenia lasting for ≥ 7 days in duration, any Grade 4 thrombocytopenia, or any Grade 5 hematologic toxicity. At least three patients in each cohort must be evaluable for hematologic toxicity.
- Non-hematologic dose-limiting toxicity will be defined as any Grade 3, 4 or 5 non-hematologic toxicity, with the specific exception of:
 - Isolated Grade 3 elevation of liver function tests (LFTs) without associated clinical symptoms, lasting for ≤ 7 days in duration.
 - Isolated Grade 3 elevation of amylase without associated clinical symptoms
 - Grade 3 hypocalcemia, hypokalemia, hypomagnesemia, hyponatremia, or hypophosphatemia which responds to medical intervention.

Definition of Maximum Tolerated Dose:

The MTD of the combination of lenalidomide, thalidomide and dexamethasone in multiple myeloma subjects shall be defined at the end of the trial, the dose with the smallest absolute value of (*posterior mean of pi-pT*) among all the tried doses *i* for which $T_i=0$ will be selected as the MTD.

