6.3.1 Study Duration

Patients who attain a CR/VGPR/PR may elect to stop treatment at any point after cycle 2 and proceed to stem cell mobilization and transplantation. Patients who achieve less than a CR/nCR or patients, or who do not proceed to SCT, may receive up to 8 cycles of the combination therapy. Patients who progress will be removed from therapy. If a patient in CR/nCR/VGPR then patients receive up to 2 cycles beyond best response or up to 8 cycles at physician discretion and then proceed to maintenance therapy.

After 8 cycles, patients who have stable or responding disease to treatment and have an acceptable toxicity profile will be allowed to continue treatment on a maintenance schedule described below until disease relapse, unacceptable toxicity, withdrawal of consent or no further clinical benefit is experienced. Doses of thalidomide, lenalidomide, or dexamethasone may be interrupted or reduced in an attempt to manage toxicity at physician discretion.

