6.4 Maintenance Therapy

Maintenance therapy consists of lenalidomide at the dose level tolerated at the completion of cycle 8 and thalidomide at 50 mg daily. Dexamethasone may be continued in the maintenance phase at physician discretion. Patients unable to tolerate either lenalidomide or thalidomide in combination during the maintenance phase may continue on either agent at the investigators discretion.

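### Thalidomide dosing text conflicts for patients with prior toxicity: maintenance is set at 50 mg daily whatever was tolerated, the second neuropathy cut has two end points not matched to dose, and the cycle 8 anchor is missing for early entrants

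*Combined protocol and SAP*

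**What the plan says.** **Starting doses.** Table 6-1 (section 6.2) gives Level -1 as "50 mg Thalidomide daily 40 mg dexamethasone" and Levels 1 and 2 as "100 mg Thalidomide daily 40 mg dexamethasone". Level 3 uses thalidomide 200 mg. Section 6.3 describes the MTD regimen for the added lenalidomide-refractory cohort with thalidomide 100 mg daily.

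**Neuropathy (Appendix B, thalidomide item 3).** After grade 2 or higher neurotoxicity the drug is held, and "then Thal may be restarted at 50% of previous dose". On recurrence, "another 50% reduction can occur after symptoms resolve to 50 mg every day or every other day".

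**Other toxicity (Appendix B, thalidomide items 2 and 5).** A second grade 3 event leads to a restart at half dose. After that, "If grade 3 AE occurs a third time drug will be discontinued and the pt followed until the AE resolves or stabilizes". Somnolence also leads to a 50% cut.

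**Maintenance (section 6.4).** "Maintenance therapy consists of lenalidomide at the dose level tolerated at the completion of cycle 8 and thalidomide at 50 mg daily". A later sentence lets patients who cannot tolerate the combination while on maintenance continue on one agent.

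**Entry to maintenance (section 6.3.1).** For patients in CR, nCR or VGPR, "patients receive up to 2 cycles beyond best response or up to 8 cycles at physician discretion and then proceed to maintenance therapy".

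**Background (section 1.3.3).** Neuropathy is described as potentially irreversible and generally a result of months of use. "Usually treatment with thalidomide should only be reinitiated if the neuropathy returns to baseline status".

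**The concern.** Three sets of instructions govern thalidomide in a patient who has already had toxicity, and they do not agree.

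- Item 3 states a percentage and two absolute end points in one sentence. They cannot both be met on every dosing path.
- Section 6.4 treats the two drugs differently. Lenalidomide follows the patient's tolerated dose. Thalidomide does not, and no exception is written for a patient whose thalidomide was cut below 50 mg/day or stopped. The single-agent clause refers to intolerance arising during maintenance, so read literally it applies only after re-exposure.
- The lenalidomide anchor assumes eight completed cycles, which section 6.3.1 does not require.

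The stake is mainly patient safety and consistent conduct: two physicians following the text could give different doses to the same patient with recurrent neuropathy. The literal rise at maintenance also coincides with a lighter listed schedule. Section 6.7 lists a directed neurologic examination on day 1 of each treatment cycle from cycle 2, but not among the maintenance visit procedures.

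**Working it through.** **Inputs.** Starting doses of 50, 100 and 200 mg/day (Table 6-1); halving at each neuropathy event (item 3); stated end points of 50 mg every day (average 50 mg/day) and 50 mg every other day (average 50/2 = 25 mg/day); maintenance at 50 mg/day (section 6.4).

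**Step 1: can the stated end points be reproduced?** Dose after the first event = start × 0.5. Dose after a true second halving = start × 0.25.

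- 200 × 0.25 = 50 mg/day, which is 50 mg every day.
- 100 × 0.25 = 25 mg/day, which is 50 mg every other day.
- 50 × 0.25 = 12.5 mg/day, which is neither.

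So each end point is the exact second halving for one starting dose, and Level -1 has none.

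**Step 2: what does each option do at the second event?** Change = (end point − dose then taken) / dose then taken.

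| Path before the second neuropathy event | Dose then taken (mg/day) | 50 mg every day | 50 mg every other day |
|---|---|---|---|
| Start 200, one neuropathy cut | 100 | −50% | −75% |
| Start 100, one neuropathy cut | 50 | 0% | −50% |
| Start 50, one neuropathy cut | 25 | (50 − 25)/25 = +100% | 0% |
| Start 200, one 50% cut for another toxicity, one neuropathy cut | 50 | 0% | −50% |
| Start 100, one 50% cut for another toxicity, one neuropathy cut | 25 | +100% | 0% |

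Item 3 does not say which column applies to which row. In the two rows at 25 mg/day, neither column is a reduction.

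**Step 3: what does the switch to maintenance do?** Change = (50 − prior average dose) / prior average dose.

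| Prior average dose (mg/day) | Change at 50 mg daily |
|---|---|
| 200 | −75% |
| 100 | −50% |
| 50 | 0% |
| 25 | +100% |
| 12.5 | +300% |
| 0 (discontinued under item 2) | restart |

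The +100% row can be reached by following the rules exactly from the 100 mg dose in section 6.3: 100, then 50, then 50 mg every other day, then 50 mg daily at maintenance.

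**Step 4: does the cycle 8 anchor always exist?** Under section 6.3.1 a patient in CR, nCR or VGPR may stop combination therapy up to 2 cycles after best response. If best response comes by cycle 5, that is at most 5 + 2 = 7 cycles. Such a patient can enter maintenance without completing cycle 8, and section 6.4 then defines no lenalidomide dose.

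**The case against.** The best defence is that the guidance is discretionary and mostly workable.

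- Section 6.11 calls the modification tables suggested rather than required. Section 6.3.1 allows any of the three drugs to be interrupted or reduced at physician discretion, and section 6.8.3 allows individual thalidomide reductions. Item 3 is permissive in its wording.
- After cycle 8, section 6.3.1 admits to maintenance only patients whose toxicity is acceptable. Section 6.12 ends treatment for adverse events that rule out continuing. Section 6.8 (Concomitant therapy) contemplates single-agent maintenance.
- At the 100 mg dose in section 6.3, every-other-day dosing is an exact second halving. An increase under item 3 needs a patient already averaging 25 mg/day, and using a sentence about a reduction to raise a dose would contradict its own words.

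Most of this stands, and it rules out several stronger readings that a reader might infer:

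- **That item 3 ends at 50 mg daily for everyone.** The sentence also offers every other day.
- **That maintenance generally raises thalidomide after toxicity.** A patient cut from 200 to 100 mg is lowered, and one cut from 100 to 50 mg is unchanged.
- **That the protocol forces an increase or a restart.** The discretion clauses prevent that.
- **That the time-to-event endpoints are harmed.** The response criteria count progression on or off therapy, so stopping thalidomide is not itself an event, and the documents give no basis for estimating how many patients would be affected.

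The defence does not remove the conflict. The suggested status in section 6.11 attaches to the modification tables, whereas the 50 mg daily in section 6.4 is the stated treatment regimen. Discretion lets a physician depart from contradictory text; it does not say what the text means.

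**Conclusion.** The inconsistency is real but narrower than a first reading suggests.

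- **Maintenance.** Taken literally, section 6.4 doubles the average thalidomide dose of a patient on 50 mg every other day (25 to 50 mg/day) and restarts it after discontinuation under item 2. It holds or lowers the dose for anyone on 50 mg/day or more.
- **Item 3.** The two schedules are not matched to the current dose. One permitted reading is a 0% change for a 100 mg start, and neither option reduces the dose of a patient already averaging 25 mg/day.
- **Timing.** The lenalidomide anchor is undefined for patients who enter maintenance before completing cycle 8.

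This rests on averaging every-other-day dosing to 25 mg/day and on applying each 50% cut exactly. The documents do not give capsule strengths, so whether 25 or 12.5 mg could be dispensed daily is unknown. Sample size, stopping boundaries and error rates are unaffected. The reason to act is that the rules conflict on a safety matter which section 1.3.3 itself describes as potentially irreversible.

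**What to change.** By amendment, the sponsor should reconcile sections 1.3.3, 6.2 (Table 6-1), 6.3, 6.3.1, 6.4 and 6.11 with the thalidomide items in Appendix B, so that:

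1. the percentage and the end points in item 3 agree for every thalidomide dose the protocol can produce;
2. the maintenance thalidomide rule does not conflict with a prior reduction or discontinuation under Appendix B;
3. the lenalidomide maintenance anchor is defined for patients who enter before cycle 8.

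The doses and the clinical rules are for the sponsor to set, and none is proposed here. The cost is a few sentences, with no added patients or data.
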